Physical Activity in the Medical Workplace: A way to improve physical and mental well-being?

NCT02794727

04 April 2019

Title: Physical Activity in the Medical Workplace: A way to improve physical and mental well-being?**Abstract**

Many Americans do not meet the physical activity guidelines and the majority of Americans are overweight or obese. Decreased physical activity is not only associated with multiple chronic medical conditions, including obesity, but also with depressed mood, and other negative emotions. As many employed adults spend a great deal of time at work where we are predominantly sedentary, strategies to increase physical activity at work are being pursued to help improve the physical and mental health of Americans. This 17 week randomized controlled trial will investigate changes of occupational physical activity in three groups: those provided with a FitBit® but not able to monitor their activity level, and those provided with activity goals and individual physical activity challenges, and those who do not use a FitBit®. We hypothesize that providing awareness of occupational physical activity level as measured by an accelerometer (FitBit®) will increase occupational physical activity. In addition, we hypothesize that as measured by the SF-36® and perceived stress scale questionnaire measures of emotional health will also improve.

Specific Aims/Objectives

1. We hypothesize that utilizing a FitBit® to monitor activity level (i.e. Step count); will lead to increased occupational physical activity (OPA).

Background

Less than a third of American adults reach the CDC physical activity guidelines [2]. Many of our occupations are sedentary and lead to decreased time in physical activity [3, 4]. Being sedentary is associated with multiple adverse health outcomes, including obesity [5, 6]. In an effort to improve health, many workplaces and schools are attempting interventions to help increase occupational physical activity (OPA) [7].

In addition to general health benefits, participation in regular physical activity has been associated with decreased risk of depressive symptoms [8]. A review of school and workplace interventions to increase physical activity found that after the intervention there were improvements in self-esteem, self-efficacy, satisfaction and commitment while there were decreases in anger, difficulty concentrating, fatigue, stress and feelings of sadness and depression [7]. A variety of interventions have been tried in numerous settings, many using self-report or questionnaires of physical activity [7, 9]. Interventions utilizing pedometers and providing activity goals have been successful at increasing OPA at a multi country university study [9]. Correlations with the improvement in OPA with markers of physical and mental well-being were not performed [9].

Our goal with this study is to further investigate the efficacy of workplace interventions to improve physical activity as measured by an accelerometer (FitBit®). The FitBit® has been previously validated as a reliable step counter [10]. Our workplace includes many different occupations and we will investigate if participant knowledge of OPA level leads to improved OPA levels. Further, if there is an increase in OPA, is this associated with weight loss and with decreased feelings of sadness and depressive symptoms.

Project Design/Methods**Study Subjects**

All employees within divisions of DOM will be eligible to participate in the present study. This will be a 17 week randomized controlled trial with a 4-week run-in phase, a 12 week randomized intervention phase, and a 1 week post intervention phase.

Inclusion criteria:

1. Be between 18 – 65 years of age
2. Be a Mayo Clinic employee at 0.75 FTE or more
3. Have not used an activity monitor within 2 weeks of study entry
4. Agrees not use any other activity monitor during study participation
5. Not be pregnant by subject self-report
6. Have a stable weight-defined as self-reported weight that has not changed more than 10% in the past 3 months
7. Not have any previous history of joint problems that limit free movement, as determined by the PI
8. Be able to participate fully in all aspects of the study
9. Have understood and signed study informed consent

Exclusion criteria:

1. Have a known history of any condition or factor judged by the investigator to preclude participation in the study or which might hinder adherence or skew data collection – such as a position where they predominantly provide transport as part of their job

Study Groups

We propose to recruit, consent and screen 270 subjects through IRB approved contact materials such as e-mail, phone call, flyers, and classified advertisements in order to randomize 135 to study. All subjects who respond will be pre-screened for inclusion and exclusion criteria via a telephone pre-screen. Those who meet criteria will be invited to a consent visit followed by a study screening visit. After consent and screening has taken place, subjects who meet all study entry criteria will be invited to participate in the study.

When a subject is found to be eligible for the study, they will be asked by the study staff to create a google email which will be used by the study to download their weekly fitbit data. Subjects will not have access to this google email password since they need to remain blinded to the fitbit data during the trial, but the email and password will be returned to them at the end of the study and they will be shown how to change their password so that it can remain confidential. They will also be informed that they will be able to keep the fitbit assigned to them once they complete all 17 weeks of the study. The google email is used by the study staff to download their weekly data in an online account and this is the outcome data needed for the study.

The first 20 subjects enrolled in the study will be asked to participate in an additional validation phase. For this validation phase of the subject will be asked to wear a FitBit® on both wrists and walk on a treadmill, located in the DAHLC, while the study coordinator records their steps manually using a clicking device. The subject will be asked to walk for 5 minutes at 0.9 MPH, followed by 5 minutes at 3.0 MPH and 5 minutes at 4.0 MPH. They will then be asked to continue on with the blinded run-in phase.

All eligible subjects will be invited to participate in 4-week run-in phase using the FitBit® while at work and be blinded to the FitBit® daily activity recording. This run-in phase will be used to collect baseline OPA data for each subject. During the run-in phase subjects will be provided with a FitBit® but will not be made aware of their OPA level. FitBit® accounts will be created and maintained by the study team. The FitBit® itself will have the displays covered so that it will not be available for the subject to read during the blinded phase(s). During this time subjects will be asked to wear their FitBit® while working and leave the FitBit® at their desk at the end of

each day. The FitBit® will be collected by study staff at the end of the subjects' workweek. During which time the coordinating staff will download the weekly data and recharge the devices. They will then return the devices to the subjects at the beginning of their work week. At the end of the 4-week run-in-phase (baseline) they will be randomized into one of the three 12 week intervention arms using a computer-driven random number generator created with the help of statistician. The groups to which they will be randomized will be:

1. **Group 1** (control group)- participants will be blinded to their OPA during the entire study (run-in and randomized intervention phases).
2. **Group 2** (intervention group)- This group will be able to access their FitBit® activity data by viewing the display, therefore they will be unblinded during the randomized intervention phase (and blinded during the run-in phase). Participants will be given a specific OPA target based on the results from the run-in phase. The principal investigator or one of the co-investigators will meet with the participants randomized into this intervention group. The investigator will meet with subjects within 1 week of the study visit (baseline and week 6). Based on the physical activity tracked during the baseline period, instructions will be provided to increase the OPA by 5 % a week as determined by their average OPA at their last study visit. If at the post 6 week study visit their OPA remains <5000 steps per day, we will encourage the same 5% per week increase in OPA. Various methods such as taking steps as much possible prior to taking elevators, lunch time walks, walking breaks, and walking meeting of non-patient related topics will be suggested. The daily FitBit OPA activity will be downloaded weekly by the study staff and a print out of the weekly activity will be placed in the subjects study files for use by the investigators during these feedback sessions with the subject.
3. **Group 3** (no FitBit® Group) – No FitBit® during the 12 week randomized intervention phase.

As in the run-in phase, subjects will be asked to wear their FitBit® while working and leave the FitBit® at their desk at the end of each day. The FitBit® will be collected by study staff at the end of the subjects workweek. During which time the coordinating staff will download the weekly data and recharge the devices. They will then return the devices to the subjects at the beginning of their work week.

All subjects will be contacted for a final study visit via the telephone at 1 week post the randomized intervention.

At baseline, and 6 weeks after they start the randomization intervention and at the end of the randomization phase (12 weeks) all study participants will be asked to complete the perceived stress scale, the SF 36 scale and be measured by the InBody 770®. In addition, subjects in group 2 will meet with one of the study investigators. OPA during the first 6 weeks of intervention period would be reviewed. For participants who have met the goal OPA, only feedback to continue the OPA would be provided. For participants who have not met the goal OPA, further instructions will be provided to improve the OPA.

Sample Size

A sample size of 42 in each group will have 80% power to detect a difference in the mean of 2.5% weight loss difference between a Group 1 and Group 2, or Group 1 and Group 3, or Group 2 and Group 3 assuming that the common standard deviation is 4.00 using a two group t-test with a 0.050 two sided significance level as shown below. Adding a control will not change the sample size required in each group since, there will only be a comparison between only two groups at a time.

Two group t-test of equal means (equal n's)				
Column	1	2	3	4
Test significance level, α	0.050	0.050	0.050	0.050
1 or 2 sided test?	2	2	2	1
Group 1 mean, μ_1	2.500	2.500	2.500	2.500
Group 2 mean, μ_2	5.000	5.000	5.000	5.000
Difference in means, $\mu_1 - \mu_2$	-2.500	-2.500	-2.500	-2.500
Common standard deviation, σ	6.000	5.000	4.000	4.000
Effect size, $\delta = \mu_1 - \mu_2 / \sigma$	0.417	0.500	0.625	0.625
Power (%)	80	80	80	80
n per group	92	64	42	33

From the research studies conducted at Mayo Clinic in the past, there is a 6 – 7% drop out rate in the recruitment. To account for this drop-out rate, we propose to include 45 subjects in each arm of the study. We acknowledge that achieving a 2.5 % change in body weight might not be clinically feasible. We propose to run this study as pilot study to estimate the amount of weight loss, change in body fat percentage and improvement in satisfaction level. We propose to run a larger randomized controlled study using this as preliminary data.

Data Collection

All data will be collected by the Study coordinator or by an online RedCap survey emailed to the subject. After consent and screening is completed, Perceived stress scale questionnaire and SF-36®, height, weight and InBody 770® scan will be collected, followed by providing the participant with his/her FitBit® for the run-in-phase. After the 4-week run-in-phase is completed, subjects will come in for randomization to one of the groups described above.

FitBit® devices will be collected on a weekly basis to download activity levels and charge the devices. A FitBit® account will be created for each study participant by the research coordinator to allow us to track activity level while keeping all participants blinded during the run-in-phase and group 1 blinded during the randomized intervention phase . FitBit® display will be hidden from the wearer for Group 1. For Group 2, The online program will allow us to limit the information the FitBit® wearers see so that the FitBit® can be specific to the goals set by the investigators. We will repeat the perceived stress scale questionnaire, SF-36® and InBody 770® after 6 weeks in the intervention phase and at week 12 which is the end of the randomized intervention phase.

One week after the completion of the study, we will complete one phone visit with each of the subjects.

Subjects must wear the FitBit® at work for a minimum of 48 days out of the possible 60 days during the randomization phase.

Data Handling

To ensure the confidentiality of the subjects participating in the present study; no names, social security numbers, hospital or clinic numbers will be included in the biostatistics databases. Names, addresses, telephone numbers, and any other information needed for recruitment, study involvement, and tracking will be obtained and maintained by the project personnel in a secured server with limited access. In addition, all study data (i.e. data collection forms as well as regulatory paperwork) will be maintained on a secure file server or in locked research data storage rooms to which only designated project staff will have access. All computer files and systems will be password protected and accessible by authorized personnel only. Data entry and transfer will be performed by the study staff after IRB approval.

Data Analysis

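### Run-in OPA is known for every subject before randomisation, but no stratification and no baseline adjustment is stated, so the Group 2 v Group 1 OPA comparison gives up precision

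*Combined protocol and SAP*

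**What the plan says.** All references are to the combined protocol and SAP.

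- **Aim.** Specific Aims/Objectives lists one hypothesis: using a FitBit to monitor steps increases OPA.
- **Who enters.** Study Subjects: "All employees within divisions of DOM will be eligible to participate in the present study". The Background adds "Our workplace includes many different occupations". No criterion limits baseline activity. The exclusion is left to investigator judgement, with one job-based example: "such as a position where they predominantly provide transport as part of their job".
- **What is known before allocation.** Study Groups: "This run-in phase will be used to collect baseline OPA data for each subject".
- **Allocation.** Study Groups places randomisation after the run-in has ended and describes the method only as "using a computer-driven random number generator created with the help of statistician". No stratum, block or minimisation factor is named anywhere.
- **Arm size.** Sample Size plans 45 per arm; Study Groups gives 135 in total.
- **Analysis.** Data Analysis gives a t-test, or a Wilcoxon rank-sum test if the data are skewed, at two-sided 0.05. It names no baseline covariate. It does not say whether OPA is compared as a follow-up level or as a change from run-in, although the Abstract speaks of changes in OPA.
- **Group 3** wears no FitBit in the 12-week phase, so only Groups 1 and 2 have OPA to compare.

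**The concern.** Staff in many different jobs are likely to differ widely in steps at work. A person's four-week run-in mean is probably the best available predictor of that person's OPA over the next twelve weeks. The plan has it for every subject before allocation but, as written, uses it neither to balance the arms nor as a covariate.

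With about 45 per arm, the two groups that carry the sole aim can start some way apart by chance. An unadjusted comparison of follow-up OPA would carry much of that gap into the result. A comparison of changes would over-correct, because people who start high tend to fall back towards the mean. The Sample Size section presents the study as preliminary data for a larger trial, so an unlucky allocation could mislead that design as well.

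**Working it through.** **1. The plan's own figure.** Inputs from Sample Size: difference 2.5, SD 4.00, two-sided alpha 0.05, power 80%. The effect size is 2.5/4 = 0.625. The exact t-test solution is 41.2, rounded up to 42 per group (power 80.8%), so the plan's 42 reproduces. For drop-out, 42/0.94 = 44.7 and 42/0.93 = 45.2, in line with 45 per arm. That calculation is for weight loss; the plan gives none for OPA.

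**2. Chance difference in baseline OPA between two arms of 45.** In SD units of run-in OPA, without stratification:

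- SE = √(2/45) = 0.211
- 95% range = ±1.96 × 0.211 = ±0.41 SD
- P(difference beyond 0.3 SD) = 2 × [1 − Φ(0.3/0.211)] = 15%
- P(difference beyond 0.4 SD) = 6%

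**3. What such a gap does to an unadjusted test.** The correlation ρ between run-in and follow-up OPA is not in the documents; I assume 0.5 to 0.8, with equal SDs. With no treatment effect, a baseline gap d shifts the follow-up difference by ρd and the change-score difference by (ρ − 1)d. In both cases the SD around that shift is 0.211 × √(1 − ρ²).

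For d = 0.41, at the edge of the 95% range:

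| ρ | shift, follow-up | type I error given d, follow-up | shift, change | type I error given d, change |
|---|---|---|---|---|
| 0.5 | 0.21 SD | 13% | −0.21 SD | 13% |
| 0.8 | 0.33 SD | 25% | −0.08 SD | 8% |

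These rates are conditional on an unlucky allocation. Averaged over all allocations, the type I error stays at 5%.

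**4. What adjustment gains.** Variance relative to an unadjusted follow-up comparison is 1 − ρ² for ANCOVA and 2(1 − ρ) for change scores. ANCOVA relative to change is therefore (1 − ρ²)/[2(1 − ρ)] = (1 + ρ)/2.

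| ρ | ANCOVA v follow-up | ANCOVA v change |
|---|---|---|
| 0.5 | 0.75 (25% less) | 0.75 (25% less) |
| 0.8 | 0.36 (64% less) | 0.90 (10% less) |

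**5. What stratification gains.** Assuming normal run-in OPA, a split at the median and balance within strata, the within-stratum variance is 1 − 2/π = 0.363. The 95% range falls to 1.96 × √(0.363 × 2/45) = ±0.25 SD.

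**6. The same imbalance as a share of low-activity staff.** The share below any cut is not given. If half of entrants are below it, two arms of 45 differ in that share by at least 10 percentage points in 34% of allocations and by at least 20 points in 7% (exact binomial). At a 30% share the figures are 30% and 5%; at 20%, 23% and 2%.

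**The case against.** The strongest reply is that chance imbalance is not bias. The plan's test is valid over repeated randomisation, stratification is optional in a self-described pilot of 135, and broad entry looks deliberate. All of that stands, and it limits the point to precision and the credibility of a single result. A change-score analysis, which the Abstract might imply, would also soften the problem, though less well than ANCOVA. The absence of stratification is read from silence: the text does not rule it out. The powered outcome is weight loss, and the documents do not quantify its link to baseline OPA.

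Three stronger readings are tempting and are not supported.

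- **That the Group 2 programme splits at 5000 steps at baseline, so that arms could differ in the programme on offer.** The condition reads "If at the post 6 week study visit their OPA remains <5000 steps per day", so it applies at week 6, after randomisation. At the start every Group 2 member is asked for the same 5% a week from their own level. If that compounds for six weeks (assumption), someone who complies from 5000/1.05⁶ = 3731 steps is at 5000 by then. A run-in cut at 5000 would not balance who meets the week-6 condition.
- **That covariate adjustment cannot help.** This depends on the first misreading. The plan has no subgroup analysis at 5000 steps, and ANCOVA on the continuous value uses more information than a two-level stratum.
- **That the planned arm sizes will usually be missed.** Under simple 1:1:1 randomisation the smallest of three arms falls below 42 in about 72% of allocations of 135. But Sample Size states 45 per arm, and a generator set up with a statistician can produce equal arms. Even under simple randomisation, mean power for the plan's 0.625 SD effect is 82.9%, against 83.5% at 45 v 45.

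**Conclusion.** The point holds as a cheap improvement. The plan states no use of run-in OPA in allocation and no adjustment for it in analysis, so a baseline gap between Groups 1 and 2, with a 95% range of about ±0.41 SD at 45 per arm, is left uncontrolled. The cost is lost precision and exposure to an unlucky allocation; a reader might infer bias on average, and there is none.

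The ±0.41 SD figure needs only the planned arm size. The variance savings rest on the assumed correlation of 0.5 to 0.8, and the gain from stratifying rests on a roughly normal baseline split near its median. None of this changes the sample size.

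One related inconsistency is separate. Within Study Groups, the Group 2 description makes the week-6 instruction depend on being below 5000 steps a day, while the later paragraph on the 6- and 12-week assessments makes it depend on whether the OPA goal was met. These two passages must be reconciled.

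**What to change.** 1. **Data Analysis.** Make the Group 2 v Group 1 OPA comparison an ANCOVA of OPA in the intervention phase, adjusted for continuous run-in mean OPA. State in advance what is done if step counts are highly skewed, since a plain Wilcoxon test would drop the adjustment.
2. **Study Groups.** State the allocation method: permuted blocks, 1:1:1, with varying block sizes, stratified by run-in mean OPA (for example low v high at a cut fixed before the first randomisation). Include the stratum or the continuous value in the analysis.
3. **Study Groups, week-6 review.** Reconcile the two Group 2 rules.

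The cost is small. There are no new data, visits or subjects: run-in steps are already downloaded weekly, and Group 2 targets already depend on them. The statistician prepares two blocked lists. The downside is that the run-in mean must be calculated before the randomisation visit, and incomplete final blocks may leave arms a few subjects away from exactly 45. If only one change is made, the ANCOVA matters more.

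### No randomised contrast isolates awareness of step count, although the hypothesis, the aim and the background question all credit awareness

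*Combined protocol and SAP*

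**What the plan says.** Three statements give the reason why OPA is expected to rise.

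- Abstract: "We hypothesize that providing awareness of occupational physical activity level as measured by an accelerometer (FitBit®) will increase occupational physical activity".
- Specific Aims/Objectives, the single listed aim, on using a FitBit: "to monitor activity level (i.e. Step count); will lead to increased occupational physical activity (OPA".
- Background: "we will investigate if participant knowledge of OPA level leads to improved OPA levels".

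None of the three mentions a target, coaching or advice.

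The arms are defined under Study Groups. For Group 1, "participants will be blinded to their OPA during the entire study". Group 2 sees the display. In addition, "Participants will be given a specific OPA target based on the results from the run-in phase", with an instruction to increase OPA by 5% each week and a list of suggested ways to walk more. Around baseline and again at week 6, "subjects in group 2 will meet with one of the study investigators"; those who have not reached the goal by week 6 get further instruction. Group 3 has no FitBit during the 12 randomised weeks.

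Two other statements are broader. The abstract describes the active arm as "those provided with activity goals and individual physical activity challenges", and the Background gives the overall goal as to "further investigate the efficacy of workplace interventions to improve physical activity as measured by an accelerometer".

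**The concern.** The stated cause and the randomised difference do not match. The plan says that knowing one's step count is what should change behaviour. What it randomises against blinded wear is knowing the count together with an individual goal, a weekly increase, meetings with an investigator and practical advice. Any of these added elements could raise step counts without help from the display. The Background gives a reason to take that seriously: the successful precedent that it cites combined pedometers with activity goals.

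At stake is the conclusion that may be drawn from the main activity comparison. A positive Group 2 v Group 1 result could be credited to awareness when targets or coaching produced it. The Sample Size section says that the results will serve as preliminary data for a larger randomised study, so a wrong attribution could also shape the choice of intervention there.

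**Working it through.** **Step 1. What each arm has during the randomised phase** (Study Groups and Data Collection sections).

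| Element | Group 1 | Group 2 | Group 3 |
|---|---|---|---|
| Wears FitBit at work | yes | yes | no |
| Sees own step count | no | yes | no |
| Individual OPA target, 5% weekly increase | not described | yes | not described |
| Investigator meetings around baseline and week 6 | not described | yes | not described |
| Suggestions for walking more | not described | yes | not described |
| FitBit-measured OPA available | yes | yes | no |
| Questionnaires and InBody at baseline, weeks 6 and 12 | yes | yes | yes |

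The last four Group 2 elements before the measurement rows overlap in practice, because the meetings appear to be how instructions and advice are delivered. Counting them as one element (goal-directed coaching) or as several does not alter what follows.

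**Step 2. What the contrasts estimate.** For any outcome, let b be the mean without a device, W the effect of wearing a blinded device, and P the joint effect, on top of wearing it, of display, target and coaching. Then:

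- Group 1 mean = b + W
- Group 2 mean = b + W + P
- Group 3 mean = b

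The three pairwise contrasts are:

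- Group 2 − Group 1 = P
- Group 2 − Group 3 = W + P
- Group 1 − Group 3 = W

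P is defined as a joint effect, so nothing is assumed about whether its parts add up. The effect of awareness would be the mean of a group with the display only, minus the Group 1 mean. No arm supplies the first term. The planned t-test or Wilcoxon test (Data Analysis) compares groups and cannot divide P.

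**Step 3. Which contrast bears on OPA.** Group 3 has no device in the randomised phase, so it has no FitBit-measured OPA there. Of the three contrasts, only Group 2 − Group 1 can address the OPA hypothesis. For weight, SF-36 and perceived stress all three contrasts can be computed, but by Step 2 none of them isolates awareness.

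**Step 4. How much the added elements ask for.** The weekly instruction is 5%. Over the six weeks to the second meeting:

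- linear on a fixed base: 1 + 6 × 0.05 = 1.30, or +30%
- compounded: 1.05^6 = 1.340, or +34%

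The text does not make clear which applies. Either way this is what participants are asked to do. It is not an expected effect, and it says nothing about the share due to awareness. It shows only that the target is a substantial element.

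**Step 5. The plan's own sample size.** With a 2.5-point difference in weight loss and SD 4.00, the standardised effect is 2.5 / 4.00 = 0.625. A two-sided t-test at 0.05 with 80% power needs 41.2, rounded up to 42 per group (power 80.8%), as stated. Allowing for 6% drop-out, 42 / 0.94 = 44.7, rounded up to 45, and 3 × 45 = 135. The figure reproduces. It concerns weight, so it does not bear on the attribution of an OPA effect, and rewording the aim leaves it unchanged.

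**The case against.** The strongest reply is that the documents, read as a whole, openly describe a package. The sentence of the abstract just before the hypothesis says that the active arm has goals and challenges. The Background cites a goals-plus-pedometer precedent and sets the broader goal of studying workplace interventions. Data Collection says that what Group 2 sees can be tailored to the investigators' goals. On this reading awareness is shorthand for monitoring with goals, and testing a multi-component intervention is a legitimate choice. The trial is also described as a pilot, though the quantities named there are weight loss, body fat and satisfaction.

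Much of this stands. The package itself is not at fault, and Group 2 v Group 1 answers the broader goal. But describing an arm does not supply an awareness contrast. The hypothesis, the only listed aim and the stated question all still name awareness, monitoring or knowledge, and nothing tells the reader to take these as shorthand.

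Four stronger readings are tempting, and the documents do not support them:

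- A reader might infer that awareness is not tested at all. Group 2 v Group 1 tests a bundle that includes it; what is missing is a contrast that isolates it.
- A reader might infer that the plan promises a test of awareness by itself. No section says so.
- A reader might infer that a positive result will be reported as an awareness effect. The documents contain no interpretation or reporting rule, so it can only be said that it could be.
- A reader might want a range for the share due to awareness. No figure in the documents yields one.

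**Conclusion.** The point holds as a mismatch between the stated cause and the randomised difference. It affects all three statements of the activity question and the only contrast that can answer that question with FitBit data. A positive Group 2 v Group 1 result would meet the written hypothesis even if awareness added nothing. The size of any misattribution is not identifiable from this design, and no number is put on it.

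The conclusion rests on two assumptions: that Group 1 receives no target, coaching or walking advice, since none is described for it, and that Group 3 contributes no FitBit-measured OPA after randomisation. The trial remains valid for the package as a whole. The correction should be made, but it concerns what may be concluded and does not call the conduct of the trial into question.

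**What to change.** Restate three places and add one sentence. Suggested wording:

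- Abstract hypothesis and Specific Aim 1: *Compared with blinded FitBit wear, a package of visible FitBit, individual step target and investigator coaching increases OPA.*
- Background question: *Does this package, compared with blinded wear, increase OPA?*
- Data Analysis: *Group 2 v Group 1 estimates the effect of the package and is the only contrast with FitBit-measured OPA in both arms during the randomised phase. It supports no conclusion about awareness alone.*

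The cost is a narrower claim. Arms, visits, tests and sample size are unchanged.

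A display-only arm would be needed to keep the awareness claim, and it is not proposed here. At 45 per arm it would take 4 × 45 = 180 participants instead of 135. Splitting 135 over four arms gives 33 or 34 each. After 7% drop-out that leaves 33 × 0.93 = 30.7 or 34 × 0.93 = 31.6 per arm, and power for the plan's own weight difference falls to about 67% to 69%.
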